4.3 Study Enrollment Procedures

This is a real-world implementation study with minimal interaction between the study team and patients. To address recent virtual visits in primary care due to COVID-19 and for the safety of the study team, study methods were developed to adapt virtual patient recruitment and e-consent during existing virtual visit processes. An in person consenting process is also available for in person clinic visits, when safe and appropriate, and will be supported by a study team member present at recruiting clinics.

Study team will review clinic schedules routinely for visits scheduled the next day and will flag potentially eligible patients and will discuss the list with the health care team. These patients will be introduced to the study opportunity by care team members during routine clinic visits.

- Consenting in person: If the patient is interested, they will be roomed with a study team member who will confirm study eligibility and provide written informed consent. If the patient is eligible and provides consent, the study team will share a secure message with a link for the Pathway App with the patient and the patient will be able to activate the Pathway App and start entering data. The secure message will be shared with the patient via AAH's secure patient portal. Or through an email for patients who have not activated their portal. The invitation message in the email will include an individualized link to download the App with a unique code specific to that patient to ensure security.
- e-Consenting virtually: If the patient is interested, the care team member will inform the research team, who will confirm eligibility and send a secure invitation to the patient (AAH patient portal or email with unique link and code). The invitation message includes a link to start the e-consenting process and that includes study contact information to allow patients to reach out to the study team with any questions during e-consenting or during the study. The link in the message will direct the patient to start the e-consenting process. The patient will not be able to download the app until they have completed the e-consenting process. Patient e-consent will be obtained in REDCap using a finger or stylus-directed signature on the mobile phone, with data including attestation of individual identity and time and date of signing. Upon completion, participants will be able to download a pdf copy of the signed e-consent form. The patient will then be invited to download the Pathway App via another secure message with a link including details for the patient to activate the mobile app and start entering data.

4.4 Pathway Platform

The Pathway Platform consists of three components:

4.4.1 Pathway App

Pathway is a mobile application designed to gather health information related to the management of depression to enhance patient clinical engagement and guide patient care. The patient facing interface includes a digital assistant that allows patients to interact with the Pathway Platform in a chat-based conversational text interface. The information collected from the patient is intended to assist the care team in managing the patient's depression through enhancing measurement-based care and shared-decision making - enhancing patient-provider engagement and ultimately patient outcomes. The study will deploy the most recent iteration of the Pathway Platform. Earlier iterations were piloted in four primary care clinics.¹⁶ Feedback from this pilot was used to enhance Pathway Platform functionality. The current iteration of the Pathway Platform, which is the version that will be used in the implementation study described in this protocol, prompts patients to complete four scales to assess depression status biweekly (Patient Health Questionnaire [PHQ-9] and Perceived Deficits Questionnaire-Depression [PDQ-D5]), quality of life (World Health Organization- Five Well Being Index [WHO-5]), and cognition (Digit Symbol Substitution Test [DSST]).^{7,17,18,19} The Pathway Platform also includes a daily evening check-in with the patient to collect information on medication adherence and side effects. Patients reporting side effects related to sleep are prompted to complete the PROMIS Sleep Disturbance 6a and patients reporting side effects related to sexual dysfunction are prompted to complete the Arizona Sexual Experience Scale (ASEX).^{20,21} An optional functionality of the Pathway Platform is to set and track goals using the Goal Attainment approach adapted for depression during clinic visits with a healthcare provider.²² In addition, the Pathway Platform includes patient facing education for the patient on how to use the Pathway Platform to collect data as well as how to prepare for a visit with health care providers, set and assess progress towards goals and self-management. For purposes of evaluating this implementation study three additional scales assessing patient-provider engagement and functional improvement will be deployed through the Pathway Platform at baseline and subsequently every 6 months until the end of the study (Patient Activation Measure - 13[PAM-13], CollaboRATE, and Work and Social Adjustment Scale [WSAS]).^{23,24,25}

4.4.2 Electronic Medical Record integration

Data collected in the Pathway Platform is electronically transmitted and stored in the patient's EMR. This data is accessible to the care team and provides a longitudinal summary that may assist in decision making and depression management. Providers can view this data either before or during the patient visit and use it to discuss future depression management.

4.4.3 Educational Scaffolding

An online Educational training program was developed using evidence-based medicine building

on measurement-based care and shared-decision making concepts as they relate to depression management. Educational material describes how the Pathway Platform can help care team members in clinical processes related to these process improvement measures. In clinics using a collaborative care model additional education material specific to this care model is provided. Educational material housed in an online resource center which includes reading material, presentations, and videos. Additionally, up to three audit and feedback sessions will be conducted for each participating clinic. The objectives of audit and feedback sessions are to benchmark performance measures, including shared decision making, reflect on current clinical practice and improvement strategies, and setting team-based action plans. Care team members who manage depression must complete specific training before they are able to enroll patients and begin using the Pathway Platform.

A training manual was also developed for patients. The manual describes the Pathway Platform functionality, as well as, how to use and interpret the data collected.

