3.1 Performance among participating clinics post-implementation

The Pathway Platform will be implemented in up to 20 primary care sites within the Advocate Aurora Health system and enroll a total of 200 patients for six-month duration. The visit where the patient has been onboarded to the Pathway Platform will be the enrollment visit (Figure 1). During the post- implementation period, data on patient outcomes will be collected through the Pathway Platform. At the end of the study an electronic and manual chart review for patients using the Pathway Platform will be conducted among participating clinics and performance related to measurement-based care, shared decision making and collaborative care, where applicable, will be assessed over the post-implementation period.

3.2 Retrospective Assessment: pre-implementation performance at the clinic level (before Pathway Platform implementation)

To assess Advocate's primary care sites performance pre-implementation, an electronic and manual chart review will be conducted from the same Advocate primary care clinics participating in the implementation study. Patients with a clinic visit at least 6 months prior to implementation (index visit) of the Pathway Platform and meeting the inclusion criteria for enrollment in the study, will be included in this analysis (figure 1). Patient history will be evaluated for three months prior to index visit to confirm eligibility. The goal is to capture patients with a new start, dose adjustment or switch of an antidepressant medication 6 months prior to the implementation index date (three-month inclusion window for patient identification). Six months of patient history will be “retrospectively” collected for this baseline patient cohort to assess the primary outcome, defined as PHQ-9 utilization, and other secondary outcomes outlined in the protocol. This analysis will serve as the comparison control for the primary and secondary outcomes to compare performance at the same clinics pre and post-implementation of the Pathway Platform. Depending on the number of eligible patients identified per site (20 per site), group level matching for age and sex may be conducted. The primary endpoint will be the proportion of patients with at least 2 PHQ-9 scores.

Figure 1: Study schematic

* Primary and secondary outcomes will be evaluated at 6 months, data collected beyond 6 months will be used for exploratory analysis

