4. SELECTION AND ENROLLMENT OF PARTICIPANTS

Patients will be recruited from up to 20 primary care clinics within Advocate Aurora Health that have agreed to implement the Pathway Platform. We aim to identify clinics that are representative of different geographic locations, patient populations, and care models for depression management, including behavioral health integration models. We will balance clinic diversity with feasibility to conduct this study. For example, we will only include clinics that have integrated Epic within their workflow so that the care team can easily access data collected from the patient in the Pathway Platform. We will also focus on clinics that have a large volume of patients diagnosed with depression as well as clinics that have care team members that are interested and engaged in depression care.

All care team members who care for patients with depression will be invited to participate in this implementation study and will have access to an online educational resource center. Patients fulfilling the following criteria will be eligible to download and use the Pathway Platform:

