8.4 Data analysis

For primary and secondary hypothesis testing, process measures, patient clinical outcomes, and health care resource utilization will be compared pre- and post- implementation of the Pathway Platform.

Additional patient reported outcomes will be compared among patients using the Pathway Platform only at baseline and end of study. For pre-implementation, outcomes will be assessed among patients who visited one of the study clinics at least once over the pre-implementation study period and were eligible to use the Pathway Platform, if it had been available. For the post-implementation period, the Pathway Platform will be the data source for paired t-test analysis, assessing change in continuous variables including PHQ-9 scores. Categorical outcomes will be presented as proportions and compared using Pearson Chi2 test. Continuous outcomes will be assessed for normality and presented as means and standard deviations (SD) or medians and interquartile ranges (IQR); continuous outcomes will be compared using Student's t test for independent groups. Two-tailed tests using a significance threshold of $p < 0.05$ will be used for all tests.

Exploratory outcomes: will be described among patients attending the pathway platform clinics only and will be compared between baseline, 6-month and extended follow up. Change in these outcomes overtime, including utilization analytics will also be explored. Categorical outcomes will be presented as proportions and compared using McNemars' test. Continuous outcomes will be assessed for normality and presented as means and standard deviations (SD) or medians and interquartile ranges (IQR); continuous outcomes will be compared using Student's Paired t test for single group comparison. Two-tailed tests using a significance threshold of $p < 0.05$ will be used for all tests. Goal attainment will be summarized by proportion of patients who achieve their identified goals based on the set time bound duration of the goal (i.e., GAS Score ≥ 50).^{29,30} The goal attainment scale adapted for depression yields a norm-based score (standardized to a mean of 50, SD of 10) at baseline and at the end of the time bound goal; the change from score from baseline will also be summarized.

System level performance: Process outcomes will be evaluated at the system level (all primary

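### The post cohort enters through trained, participating care team members while the pre cohort takes eligible patients of any clinician at the same clinics, which can inflate the before-after change

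*Combined protocol and SAP*

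**What the plan says.** **Post cohort.** Section 4 states: "All care team members who care for patients with depression will be invited to participate in this implementation study". Section 4.4.3 adds: "Care team members who manage depression must complete specific training before they are able to enroll patients and begin using the Pathway Platform". Under section 4.3 the study team screens clinic schedules and flags candidates, and then: "These patients will be introduced to the study opportunity by care team members during routine clinic visits". No participation rate is given.

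**Pre cohort.** Section 3.2 says that "an electronic and manual chart review will be conducted from the same Advocate primary care clinics participating in the implementation study". Section 8.4 defines the analysis set as "patients who visited one of the study clinics at least once over the pre-implementation study period and were eligible to use the Pathway Platform". Neither section places a condition on the treating clinician.

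**Balancing and analysis.** The one balancing step is optional and concerns patients: "group level matching for age and sex may be conducted" (section 3.2). The test is unadjusted: "Categorical outcomes will be presented as proportions and compared using Pearson Chi2 test" (section 8.4). The same two cohorts serve the primary outcome (at least two PHQ-9 scores in the medical record over six months, section 8.3.1) and the comparative secondary outcomes in section 8.3.2.

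**The concern.** The route into the post cohort runs through clinical staff who accepted an invitation and finished training. The route into the pre cohort does not. Patients of clinicians who stayed out can count in the before group and have no clearly described way into the after group.

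In the pre period, recording a PHQ-9 depends on clinician practice. People who volunteer for a project on measuring depression plausibly measured more already. The before rate would then include low-measuring clinicians who are largely absent from the after group, and part of the observed change would be a change of clinicians. Using the same clinics does not remove this, because the difference lies between clinicians within a clinic. Choosing clinics with engaged teams (section 4) applies to both cohorts and does not remove it either.

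Training is a component of the platform, so its effect belongs to the intervention. What is in question is who takes part.

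**Working it through.** **1. The plan's own figure.** Section 8.2 assumes 75% before and 90% after, two-sided alpha 0.05 and 80% power. With the pooled-variance formula:

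n = [1.960 × √(2 × 0.825 × 0.175) + 0.842 × √(0.75 × 0.25 + 0.90 × 0.10)]² / 0.15² = 99.5, so 100 per group.

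This matches the plan. Power at the planned 200 per group is 97.9%.

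**2. The inflation.** Let f be the share of eligible pre-cohort patients seen by clinicians who later take part. Let g be how far those clinicians' pre-period PHQ-9 utilization exceeds that of their colleagues. Then

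- all-clinician pre rate = f × p_in + (1 − f) × p_out, with p_in − p_out = g;
- so p_in = all-clinician pre rate + (1 − f) × g.

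The baseline that suits the post cohort's clinicians is p_in. Using the all-clinician rate instead overstates the change by (1 − f) × g.

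**3. Numbers.** The 75% and 90% are the plan's. The values of f and g are assumptions, because the documents give neither. The third column is the planned 15 points minus the inflation. The last column is the chance of p < 0.05 at 200 per group if the platform added nothing, so that the post rate equals p_in.

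| Share f | Inflation, g = 10 to 20 points | Change left out of 15 points | Chance of p < 0.05 with no platform effect |
|---|---|---|---|
| 100% | 0 | 15 | 5% |
| 90% | 1 to 2 | 13 to 14 | 6 to 8% |
| 70% | 3 to 6 | 9 to 12 | 11 to 30% |
| 50% | 5 to 10 | 5 to 10 | 22 to 71% |
| 30% | 7 to 14 | 1 to 8 | 40 to 96% |

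Example for f = 0.5 and g = 10: p_in = 75 + 0.5 × 10 = 80%. A post rate of 90% is then a 10-point change, not 15.

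**4. How the last column applies to the primary outcome.** Section 4.4.1 has the app prompt a PHQ-9 every two weeks, and section 4.4.2 sends app data to the medical record. Two scores in six months can be reached with little clinician action. A post rate with no contribution from the app is therefore a worst case, and the third column is the more useful one.

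**5. Secondary outcomes.** Treatment adjustments, OPTION-12 shared decision-making and behavioral health referrals (section 8.3.2) rest on what clinicians do or document in both periods. The same formula applies with each outcome's own gap, and the app does not supply these outcomes automatically. The documents give no baseline rates for them, so no size can be stated.

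**6. Power for a same-clinician comparison.** For 75% versus 90% with 200 post patients, power is about 91% with 100 pre patients and about 81% with 60. These figures keep the pre rate at 75%. A higher same-clinician baseline would leave a smaller difference and lower power.

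**The case against.** - **The app supplies the scores.** The post rate may depend mainly on whether patients answer prompts. If the app brought every clinician's patients to a similar rate, the all-clinician pre rate would be a fair baseline for a clinic-wide effect. This stands as a limit on the primary outcome. It rests on an assumption that the plan does not state, and it does not help the clinician-driven secondary outcomes.
- **Eligibility already filters the pre cohort.** Sections 4.1 and 4.2 require a recent PHQ-2 or PHQ-9. Retrospective patients need one already charted, while prospective patients can qualify at screening. This removes some patients of low-measuring clinicians from the before group and narrows the gap. It does not remove the gap: a PHQ-2 can suffice for entry, and the outcome needs two PHQ-9 scores.
- **Opting in is an inference.** The synopsis says that care team members involved in depression management will receive education, Table 1 places education before screening, and section 4.4.3 can be read as a sequencing rule for all of them. A trained nurse could introduce an untrained physician's patient. A reader might infer that patients of non-participating clinicians can never enter the post cohort, but the documents do not establish that.
- **Other analyses touch on engagement.** Section 8.3.3 looks at outcomes by providers' report use, and section 8.3.5 describes all primary care clinics. Report use exists only after implementation, and the system-level work is descriptive. Neither adjusts the comparison.

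**Conclusion.** The one-sided entry route is in the text, and nothing in the plan corrects for it. It biases the comparison only if participation within clinics is incomplete and participating clinicians already measured more. Both conditions are plausible, and neither is stated. For an assumed gap of 10–20 points the inflation is 0 at full participation, 1–2 points at a 90% share and 5–10 points at a 50% share, set against the planned 15.

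A reader might take the 11–96% rejection rates at shares of 70% down to 30% as the plan's false-positive rate. The documents do not support that, because those rates need an app that adds no PHQ-9 scores. For the primary outcome the likely harm is an overstated effect size. For treatment adjustments, shared decision-making and referrals the concern is more direct, although its size cannot be given. The point warrants a change to cohort selection and reporting. It does not invalidate the design.

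**What to change.** - **Section 3.2:** record the treating clinician at the index or enrollment visit in both cohorts. Select pre-cohort patients first from clinicians who enrolled post-cohort patients, in similar proportion per clinician where numbers allow. Fill to 200 from other clinicians at the same clinic only if needed.
- **Section 8.4:** keep the all-clinician comparison. Beside it, report the primary outcome and the three clinician-driven secondary outcomes restricted to the clinicians found in both cohorts. Patients added to reach 200 belong only to the all-clinician comparison.
- **Reporting:** give the share of each clinic's clinicians who took part. If it is close to all, the concern falls away.

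**Cost:** one extra field in the retrospective data pull, assuming that the medical record holds the visit clinician, and a few sentences of text. Clinics with few enrolling clinicians will have a smaller pool of pre-cohort patients. The restricted comparison will be less precise for subgroups, which are the plan's reason for 200 per group. Selection also has to wait until the enrolling clinicians are known.

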3.3 Study Duration

Patients will be enrolled in the study for a minimum duration of 6 months with the option to continue using the app at that time to a common study end date of January 7, 2023 (access to in-app final study evaluations will end January 21, 2023). Data from the Pathway Platform will be collected prospectively for the duration of the patient's participation. Process measures will be collected retrospectively from the EMR and through manual chart review after 6 months of enrollment and at the end of the study(post-implementation) and over a 6-month period prior to implementation (pre-implementation).

5. STUDY PROCEDURES

5.1 Schedule of events

Table 1: Schedule of evaluations

	Pre-electronic and manual chart reviews	Complete education by care team	Screening	Baseline assessment	6 month Assessment	Final assessment		
Study Day/Week:		Day -1	Day 0	Day 1	Day 168 - 172 [^]		Study end	
Visit Windows (Days):	Source		EMR/ patient scheduling	Pathway Platform	Pathway Platform	EMR and Manual Review	Pathway Platform	EMR and Manual Review
Patient electronic screening			X					
Informed consent			X					
Onboarding			X					
Demographic characteristics	X							
Number of PHQ-9 scores documented	X			X	X	X	X	
Treatment adjustments	X			X	X	X	X	
Shared decision making (OPTION-12 and CollaboRATE)	X			X	X	X	X	X
Referral to behavioral health	X					X		X
PHQ-9 scores	X			X			X	
Emergency room visits	X					X		X
Emergency room visits due to mental illness	X					X		X
Hospital admissions	X					X		X
Follow up after emergency room and hospital visits	X					X		X
Hospital admissions due to mental illness	X					X		X
Healthcare resource utilization								
Outpatient visits including phone calls	X					X		X
Outpatient visits including phone calls due to mental illness	X					X		X
Remission and response (using PHQ-9 data)	X				X		X	
PAM 13 ***				X	X			X
CollaboRATE**, ***				X	X			X
WSAS ***				X	X			X
PHQ-9				X	X	X	X	X
WHO-5				X	X			X
PDQ-D5				X	X			X
Medication adherence				X	X			X
Side effects				X	X			X
PSD-6 (only if reporting side effects of sleep problems)				X	X			X
ASEX (only if reporting side effects of sexual problems)				X	X			X
Goal Setting				X				
Goal Attainment					X			X
App analytics				X	X			X
Report analytics				X	X			X
Educational material analytics				X	X			X
In depth interviews (Patients and Clinicians)								X
Adverse Events*	X		X	X	X		X	X
Serious Adverse Events	X		X	X	X		X	X

[^]Day 168 reflects end of initial 24 week study period in which the final set of care questionnaires are available for completion (PHQ-9, WHO-5 and PDQ-D5), these expire within 3 days. Day 172; The off-boarding process is available, including the research questions (PAM-13, WSAS,

CollaboRATE), these expire after 30 days.

*If during the conduct of the study, a health care professional or patient spontaneously reports an Adverse Event or a serious adverse event to a Takeda product; such information should be reported to the sponsor. As such reports are spontaneously notified, causality of any AEs should be assumed unless there is evidence to the contrary; **CollaboRATE will also be asked within the App at Day 84 with a 30 day window for completion during patient enrollment. ***PAM 13, CollaboRATE and WSAS; the App will trigger response to these questionnaires every 6 months until study end (note; if patient completed these questionnaires within 4 weeks of study end point, they will not be re-deployed for completion at end of study).

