by Torous et al. found that while in person paper scores and app scores were strongly correlated ($r=.84$), PHQ-9 app scores were consistently higher over a 30 days period.⁶ An overall conclusion of this study was that collecting PHQ-9's through a mobile app may be more sensitive than the traditional PHQ-9.⁶ Increased consultation times are often cited as a barrier to MBC implementation.^{5,7} An app may save time as the physician will only need to review PHQ-9 instead of administering the questions during the visit. Although the validity of the PHQ-9 has been shown in studies, further research is needed to assess its ability to track outcomes of depression therapy over time.⁷ This systematic approach to treatment may have positive effects on the patient-physician relationship and enhance shared decision making.⁵

A shared decision-making (SDM) model of interaction can foster patient provider engagement as well as increase patient satisfaction.⁸ Several studies have found that individuals suffering from a mental illness want a larger part in the treatment decision making process.⁹ A common barrier for SDM is a physician choosing a treatment plan that is not mutually agreed on by both the physician and patient. This can be overcome by increasing education and further clarifying the benefits of a specific treatment plan to align with the patient's values.⁹ Incorporating a SDM model may help increase adherence to drug treatment in a primary care setting.⁸ Mobile technology can enhance SDM.

A collaborative care model (CCM) that involves behavioral health integration within primary care is another evidence-based practice that enhances depression management. Collaborative care is a systematic approach that improves patient education and integrates mental health professionals or other care extenders, such as nurses, into the primary care clinic to help primary care physicians provide treatment in conformity with evidence-based guidelines.¹⁰ CCM's have been shown to improve outcomes of patients with major depression.¹¹

We hypothesize that integrating the Pathway Platform to support measurement- based care and shared decision- making, will improve the clinic workflow, depression management, adherence to medication, patient-provider engagement and improve depression outcomes and care.

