8.3.2 Secondary outcome

Process outcomes: The following secondary process outcomes will be compared between patients attending clinics pre- and post- implementation of the Pathway Platform.

- Measurement- based care: The proportion of patients reflecting measurement-based care informed MDD treatment adjustments in their charts, defined as at least one dose change, medication switch, or add on medication during the study period. The frequency and types of treatment adjustments will also be explored.
- Shared- decision making: The proportion of patients reflecting shared-decision making, using the OPTION12 Tool framework.²⁶ The tool will be modified by adding a thirteenth domain inquiring about goal setting (Asking the patient or caregiver about goals of treatment). The frequency and domains of shared-decision making will also be explored in a manual chart review and a variable added to assess if the clinician documented asking the patient about their goals of treatment.
- Referrals to behavioral health: The proportion of patients with at least one referral will be compared. The frequency and types of referrals will also be explored.
- Follow-up after hospitalization for mental illness: The proportion of hospitalized adults who receive follow-up within 7 days of discharge and within 30 days of discharge.
- Follow-up after emergency department visit for mental illness: The proportion of adults

who receive follow-up within 7 days of discharge and within 30 days of ED visit.

- Healthcare resource utilization: Number and costs associated with hospital admission, length of stay, emergency room admissions, and encounters with outpatient clinics. Costs will be calculated using USA national average costs for inpatient and outpatient visits or using an average Advocate Health Care system cost.

Patient clinical outcomes: The following outcomes will be compared between patients attending clinics pre- and post- implementation of the Pathway Platform, keeping in mind that the number of patients with these measures in the pre- implementation patient group will be limited:

- MDD remission: The proportion of patients with PHQ-9 ≤ 5 at the end of the study period. The last measurement available during the study period will be used to calculate remission.
- MDD response: The proportion of patients with a 50% or greater reduction in PHQ-9 scores. The first and last scores available during the study period will be used to calculate response.

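### Remission and response are compared across cohorts whose PHQ-9s largely differ in mode (chart versus app), and the plan neither fixes the score source nor tests for a mode shift

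*Combined protocol and SAP*

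**What the plan says.** Section 8.3.2 lists remission and response as patient clinical outcomes and introduces them so: "The following outcomes will be compared between patients attending clinics pre- and post- implementation of the Pathway Platform, keeping in mind". The rest of that sentence warns only that few pre-implementation patients will have the measures. For remission, "The last measurement available during the study period will be used to calculate remission", against a fixed cutoff of 5. For response, "The first and last scores available during the study period will be used to calculate response". Neither definition names the source of the scores.

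Table 1 in section 5.1 does indicate a source. The 6-month and final assessments are each split into a Pathway Platform column and an EMR and manual review column. The row "Remission and response (using PHQ-9 data" is marked under the pre-implementation chart review and under the two Platform columns. It is blank in both EMR columns.

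Section 2.1 cites a study in which "in person paper scores and app scores were strongly correlated" (r = .84), yet "PHQ-9 app scores were consistently higher over a 30 days period". Under section 4.4.2, app data are sent to and stored in the EMR. Sections 4.4.1 and 6.2 have the app ask for a PHQ-9 every two weeks. Section 8.4 compares categorical outcomes by an unadjusted Pearson chi-square test. No section adjusts for mode, bridges the two modes or plans a same-mode analysis.

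**The concern.** A high correlation does not show agreement in level. A fixed cutoff depends directly on level, and so does a percentage fall. If app scores read higher and only the post-implementation cohort has them, that cohort will show less remission and less response even when true depression is the same in both.

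These two outcomes carry the clinical part of the secondary objective in section 1.2. A mode shift could hide a real benefit or look like harm, and a reader of the results could not separate it from an effect of the Platform. The issue is the level of the scores, not how many there are or when the last one falls.

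**Working it through.** **Which mode each cohort has**

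| Reading | Pre-implementation | Post-implementation |
|---|---|---|
| Table 1 row as marked | Chart PHQ-9s, no app in use | App PHQ-9s |
| EMR as common source (Design and Outcomes with 3.3) | Chart PHQ-9s, no app in use | Clinic and app PHQ-9s together |

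On the second reading, a patient who stays on the app for the 24-week period is prompted at about 24 / 2 = 12 two-week intervals. The last score in the record would then usually be an app score. Mode still follows cohort, though less completely.

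**Plan figures.** The documents give no expected rate or power for remission or response. The 100 per group in section 8.2 reproduces (75% versus 90%, pooled variance, two-sided 0.05, 80% power), but it concerns the count of PHQ-9s and does not bear on this point.

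**Size of a mode effect.** All inputs here are assumptions, because the documents give neither the shift nor the score distributions:
- the same true course in both cohorts;
- first score: mean 14, SD 5, patients below 5 excluded;
- last score: mean 8, SD 5.5, correlation with the first 0.4;
- scores rounded and held within 0 to 27;
- app score = clinic score + s, for s = 0, 1, 2, 3.

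For each s: remission = share with last + s ≤ 5. Response with both scores from the app = share with last + s ≤ 0.5 × (first + s). Response with clinic first and app last = share with last + s ≤ 0.5 × first. Deficits, in brackets, are percentage points relative to s = 0.

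| s | Remission | Response, both app | Response, clinic then app |
|---|---|---|---|
| 0 | 31.4% | 44.2% | 44.2% |
| 1 | 25.2% (6) | 40.3% (4) | 36.5% (8) |
| 2 | 19.7% (12) | 36.5% (8) | 29.4% (15) |
| 3 | 15.0% (16) | 32.8% (11) | 22.7% (22) |

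The way the minimum of 5 is imposed moves the rates by about one point.

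**Other assumed distributions** (first score mean 14, SD 4.5; correlation 0.4; s = 1, 2, 3):
- last score mean 7, SD 5: remission falls from 38.2% to 30.8%, 24.2% and 18.4%; both-app response from 52.2% to 47.9%, 43.5% and 39.3%;
- last score mean 9, SD 6: remission falls from 28.0% to 22.7%, 18.0% and 13.9%; both-app response from 37.6% to 34.2%, 30.9% and 27.8%.

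**Chance that mode alone gives p < 0.05 for remission** (chi-square, these two distributions, s = 1, 2, 3):
- 200 scored patients per group: 0.34, 0.86, 0.99 and 0.23, 0.66, 0.94;
- 80 scored pre patients (assumed) and 200 post: 0.22, 0.65, 0.92 and 0.16, 0.46, 0.77.

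**If only a share f of last post scores are app scores**, and f is unrelated to the score, the remission deficit is f times the value above. At f = 0.5 it is 0.5 × 6 = 3 to 0.5 × 16 = 8 points.

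**The case against.** The strongest objection is that the post-implementation source is not firmly established. Section 8.3.2 names none, so the app reading rests on one row of a table with some oddly placed marks. PAM-13 and WSAS, which the app delivers, are marked at study end under EMR and manual review, and the row for PHQ-9 scores has no 6-month mark. A separate PHQ-9 row is marked under both sources. The Design and Outcomes summary groups remission and response with process measures, which section 3.3 takes from the EMR and chart review. This stands as a reason not to call the confounding complete. It does not remove it, because app scores reach the EMR.

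A reader might take the section 8.4 statement that "the Pathway Platform will be the data source for paired t-test analysis, assessing change in continuous variables including PHQ-9 scores" as settling the source. It covers the paired analysis within the post-implementation period, not the between-cohort chi-square.

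A reader might also infer that app scores in this study will run higher by a known amount. The documents do not support that. Section 2.1 reports one study, over 30 days, against in-person paper forms. The plan does not say how the chart PHQ-9s were administered. The shift here could be close to zero.

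Finally, replacing the planned comparison by clinic-recorded scores alone could do more harm than good. Section 2.1 expects clinicians to review app scores rather than administer the form, so post patients with a late clinic score may be few and selected. That stands, and it makes the clinic-only version a sensitivity analysis.

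**Conclusion.** The point holds as a gap in how two secondary outcomes are measured. Chart scores on one side and wholly or mostly app scores on the other make mode largely coincide with cohort, and the plan has nothing to separate the two. If app scores run higher, as in the cited study, the bias works against the Platform on both outcomes when the post scores are app scores. It could mask benefit or suggest harm; it would not create a false benefit.

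The size is conditional on assumed score distributions and an assumed 1 to 3 point shift: about 6 to 16 points in remission and 4 to 11 in response with both scores from the app. A reader might take the 8 to 22 point response range as the expected size. It needs a clinic first score paired with an app last score, which does not arise if every post score comes from the Platform. With a shift near zero, little bias remains. The primary outcome counts PHQ-9s and does not depend on their level.

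**What to change.** In section 8.3.2 and Table 1:

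1. State the PHQ-9 source for remission and response in each cohort, and flag every score as app or clinic-recorded.
2. Compute response from a first and last score of the same mode within each patient.
3. Keep the planned pre/post comparison and add two sensitivity analyses:
   - (a) clinic-recorded scores only in both cohorts, reported with the reduced denominator and a description of who is in it;
   - (b) the app-based comparison repeated with app scores shifted over a stated range, for example 0 to 3 points. Where possible, inform the range by app-minus-clinic differences in patients with a clinic PHQ-9 close in time to the app baseline.
4. Note the limits of that bridge. Section 4.1 allows entry on a PHQ-2 alone or on a score up to 6 weeks old, so not all patients will have a usable pair. Selection on the screening score, with regression to the mean, can understate the shift.
5. Say in the plan that remission and response will be interpreted in light of (a) and (b).

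The cost is wording, a mode flag and modest extra analysis. The flag depends on the EMR extract being able to tell app entries from clinic entries, which the documents do not confirm. The clinic-only result will be imprecise and drawn from a selected subset.
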